**Subject identification, recruitment and consent:**

The subjects will be women with a diagnosis of vulvodynia, who are 18 – 45 years of age. Potential participants will be recruited from clinical and community settings in Chicago, such as the UIC campus and surrounding communities, gynecologists, certified nurse-midwives, family physicians, and women's health physical therapy practices. Recruitment will also be conducted via a link on the National Vulvodynia Association (NVA) website. We will also recruit through social media like Facebook, in addition to through phone calls and emails. We plan on recruiting up to 130 women to ensure that we have full data on 80 subjects after screening and attrition. We will strive to enroll a racially and ethnically diverse sample of women.

The consent process will be completed at the UIC College of Nursing. It may also be completed at another UIC or other private location chosen by the potential subject to go over the details of the study and informed consent. All study procedures will be conducted at the UIC College of Nursing in fully equipped, clinical research exam rooms on the second floor. The screening gynecological screening exam will take place in one of the exam rooms in the CON or at [name] office in the UIC hospital.

**Procedures:**

The research specialist (RS) will determine initial eligibility by screening potential participants during an initial telephone or in-person interview according to the inclusion and exclusion criteria. Women deemed to be eligible and interested in participating will be scheduled to go over the consent process and will then receive a gynecological screening exam by [name], a urogynecologist with expertise in changes in pelvic floor tissue related to vulvodynia, or [name], a practicing certified nurse-midwife with over 29 years of experience and a practicing acupuncturist specializing in the treatment of vulvodynia patients for 15 years. This exam will confirm the diagnosis and subtype of vulvodynia (provoked or generalized). Potential participants will also be asked to insert and remove a tampon as a standardized stimulus to provoke vulvodynia pain and women will be eligible if they report a pain level of 4 or higher. We will always use a regular size Tampax™ tampon with applicator as part of the standardized procedure. Participants determined to be ineligible after the above steps will not be able to continue study participation.

Based on the gynecological exam results, participants will be assigned to the generalized or to the provoked vulvodynia group. Eligible women will be able to start the study procedures immediately or at a future visit. Right before the first acupuncture session and once a week before an acupuncture treatment, a urine pregnancy test will be administered. If it is positive, the subject will be discontinued from the study.

Participants will be assigned at random to the experimental group, who will be treated with penetrating needles, or the control group, where the needles have a blunt tip that pinches but does not penetrate the skin. The special needles used in this study are inside an opaque insertion tube so that both the acupuncturist and participant remain blind to group assignment. The actual acupuncture needles,

**Title: DOUBLE-BLIND PHASE 2 RCT: EFFECT OF ACUPUNCTURE ON PATIENT VULVODYNIA OUTCOMES**

**RESEARCH PROTOCOL**

Dated 8/15/2017

however, are regular needles used in routine acupuncture. All participants will be informed that they will receive either real or fake acupuncture and they will not be told what kind of needles they are receiving until they complete the duration of effect portion of the study. Participants in the control group will be offered 10 free real acupuncture sessions with regular (not double-blind) acupuncture needles administered by a second acupuncturist after the end of the 17 weeks. The double blind needles are manufactured by [name], the inventor of the double blind acupuncture needle, and will be sent to us sterilized and packaged to maintain sterility.

All participants will receive 10 acupuncture session, two sessions per week over an approximately 5 week period. Each session will last about one hour. The first and last sessions only, where participants will complete the study questionnaires, are expected to last an additional 30 - 60 minutes. Each acupuncture treatment will consist of 13 acupuncture points, of which 12 points specifically treat problems with the genitals. Once the 13 needles are inserted or placed on the skin in the 13 points, they will remain in place for 45 minutes. The RS will remain with the subjects during the treatment session.

At pre-test, before the first acupuncture session, and at post-test, after the 10th acupuncture treatment, participants will be asked to insert and remove a regular Tampax™ tampon with applicator as a standardized pain stimulus, and will complete the three study measures of vulvar pain and sexual function on a computer or tablet:

- 1) PAINReportIt® computerized program to assess pain intensity as well as collect demographics and medications information
- 2) Female Sexual Function Index (FSFI) to assess dyspareunia and sexual function
- 3) Vulvar Pain Functional Questionnaire to describe the physical dimension of impairment in women with vulvodynia
- 4) At post-test, participants will also complete the Double-Blind Needle Questionnaire for the participants to report whether or not they remained blinded to the type of needle used (penetrating or skin touch placebo).

Weekly for up to 12 weeks after the 10th treatment session, the subjects will be asked to insert and remove a regular Tampax™ tampon with applicator from their vagina and complete the weekly vulvar pain diary to record their vulvar pain, so that we can determine the duration of the treatment effects.

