**Background and Purpose:**

Our long-term goal is to demonstrate the effects of acupuncture for the treatment of vulvodynia. Up to 14 million American women have vulvodynia, a debilitating pain syndrome characterized by pain (burning, irritation, stinging or rawness) in the vulva and dyspareunia that renders sexual intercourse virtually impossible and leaves these women desperate for relief. Not only are women in pain, but they often lose their partners or have relationship difficulties due to their inability to have sexual intercourse. No therapies have been proven efficacious and rapid pain relief is unpredictable and rarely possible. After exhausting Western Medicine options, these women often turn to acupuncture. But in contrast to other pain conditions, there have been no acupuncture sham control studies of vulvodynia.

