**Title: DOUBLE-BLIND PHASE 2 RCT: EFFECT OF ACUPUNCTURE ON PATIENT VULVODYNIA OUTCOMES**

**RESEARCH PROTOCOL**

Dated 8/15/2017

Specific aims are to:

Aim 1. Compare the penetrating needle group and the skin touch placebo needle group for effects on the: (a) primary outcome: vulvar pain (PAINReportIt® average pain intensity, 0-10), and (b) secondary outcomes: dyspareunia (FSFI dyspareunia) and sexual function (FSFI total). We hypothesize that controlling for baseline values, at posttest there will be statistically significant less vulvar pain (primary) and dyspareunia and better sexual function in the penetrating needle group compared to the skin touch placebo group.

Aim 2. In subjects with a clinically meaningful reduction in pain intensity (at least 1.5 points) at posttest compared to pretest, describe the duration of the acupuncture treatment and placebo effects weekly until pain returns to pretest or up to 12 weeks after posttest. We will describe the variability over time in vulvar pain intensity (0-10) after a tampon insertion-removal stimulus and thereby explore the duration of the effect by intervention group, vulvodynia subgroups, and demographic subgroups (e.g., age, race, occupation). These findings will provide insights to guide future research on initial and maintenance acupuncture for vulvodynia.

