**Anticipated risks:**

This study has minor risks. There is a small risk of mild bruising, soreness or bleeding after the real acupuncture needle is withdrawn. There is a risk that participants may experience a negative reaction from acupuncture and thereby experience worse symptoms from participation in the study. Participants may feel mild discomfort upon needle insertion, but this dissipates once the needle has been inserted. To avoid or minimize these risks only experienced licensed acupuncturists will perform the acupuncture. There is a risk that some of the questions in the questionnaires may make the participants uncomfortable, nervous or tired, but they don't need to answer any question they don't wish to answer. There is also the risk of loss of privacy or confidentiality, but we will avoid this risk as much as possible.

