**Data analysis:**

[name] will supervise all data analysis procedures. Prior to data collection and entry, a codebook will be created with the variable names, descriptions, and value codes of each variable. Missing data will be minimized through our retention efforts but are inevitable, to some degree, in any longitudinal study. We will address missing data by intention to treat analyses (ITT), using the full information maximum likelihood (FIML) approach, which has been shown to produce unbiased parameter estimates and standard errors. To begin to phenotype subjects with emotional disturbances we will explore the emotional dimension of pain at baseline and after the 10th acupuncture treatment using the well-known Pain Rating Index-Affective (PRI-A) score from PAINReportIT®.

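### Aim 2 duration depends on a weekly tampon test that a woman may skip once pain returns, and the plan neither records why a week was missed nor tests the FIML assumption

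*Combined protocol and SAP*

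**What the plan says.** Aim 2 (Specific aims) is restricted to responders: "In subjects with a clinically meaningful reduction in pain intensity (at least 1.5 points) at posttest compared to pretest". In them the plan will "describe the duration of the acupuncture treatment and placebo effects weekly until pain returns to pretest or up to 12 weeks after posttest". The measurement is tied to the stimulus: "We will describe the variability over time in vulvar pain intensity (0-10) after a tampon insertion-removal stimulus". The purpose is to "thereby explore the duration of the effect by intervention group, vulvodynia subgroups, and demographic subgroups".

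Procedures asks women to perform the insertion each week and then "complete the weekly vulvar pain diary to record their vulvar pain, so that we can determine the duration of the treatment effects". Neither section says what happens in a week when the tampon was not inserted, or whether the reason is recorded.

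The only missing-data provision is in Data analysis: "We will address missing data by intention to treat analyses (ITT), using the full information maximum likelihood (FIML) approach". The section goes on to describe FIML as giving unbiased estimates and standard errors, and attaches no condition. It does not mention the diary.

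**The concern.** The measurement and the event are linked. Procedures uses the tampon as a standardized way to provoke pain, and the inclusion criteria require a score of 4 or higher from it. Aim 2 duration ends when pain on this same stimulus is back at its pretest level. So the week that matters most for the endpoint is also the week in which a woman has most reason not to take the measurement.

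If she skips that week, or gives up the diary, nothing in the described procedure separates her gap from one caused by travel or forgetfulness. A likelihood analysis would then rest on the weeks she did record, in which her pain was lower.

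At stake is the description of how long the effect lasts, which the protocol wants to use to guide research on initial and maintenance acupuncture. If skipping or return rates differ by arm or by vulvodynia type, the descriptions by arm and type would shift too.

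**Working it through.** **No plan figure to reproduce.** The documents state no expected duration, diary completion rate or return rate. The recruitment figures (130 recruited, 80 with full data) are not at issue here.

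**The condition FIML needs.** FIML maximises the likelihood of the observed scores. It is unbiased if, given those scores, the chance of a missing week does not depend on the missing score. Stopping after a *recorded* return meets this condition. Skipping because pain has returned *without being recorded* does not.

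**Simulation of the stated method.** Every input is an assumption; none comes from the documents.

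- Change from pretest in week w: Y = a + b·w + e, for w = 1 to 12.
- a: mean −3, SD 1, limited to a reduction of at least 1.5 points. b: mean 0.4 per week, SD 0.25, floor −0.1. e: SD 0.8.
- Return: Y ≥ 0.
- Chance of a missed diary: 5% in other weeks, m in return weeks, either as isolated gaps or as permanent stopping.
- FIML: maximum-likelihood linear mixed model with random intercept and slope, 1,500 simulated women, one run per scenario. Duration = −intercept / slope.

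Reference values with nothing missed:

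- Diary continues after return: 2.9905 / 0.4069 = 7.35 weeks.
- Diary ends at the recorded return: 2.9958 / 0.4102 = 7.30 weeks. Stopping after a recorded return therefore causes no bias of note.

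Estimated duration in weeks (each range covers the two diary conventions above):

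| m | Isolated gaps | Permanent stopping |
|---|---|---|
| 5% | 7.30–7.35 | 7.32–7.39 |
| 25% | 7.43–7.46 | 7.89–7.97 |
| 50% | 7.57–7.71 | 8.73–8.84 |
| 75% | 7.84–7.90 | 9.95–10.05 |

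Excess over the matching reference, for m from 25% to 75%:

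- Isolated gaps: from 7.43 − 7.35 = 0.08 to 7.90 − 7.30 = 0.60 weeks.
- Permanent stopping: from 7.89 − 7.30 = 0.59 to 10.05 − 7.35 = 2.70 weeks.

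At m = 5%, where return weeks are missed no more often than others, there is essentially no bias. That isolates the cause.

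**Other rules on the same model (20,000 simulated women).**

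- *Kaplan-Meier to first recorded return, censored at the last diary.* The true median is 7 weeks. At m = 25 / 50 / 75% it becomes 8 / 9 / 10 with isolated gaps and 8 / 11 / more than 12 with permanent stopping.
- *Every missed week counted as return.* The 12-week restricted mean is 6.13 to 6.17 weeks against 7.48 true, whatever m is. In this model a missed return week is scored correctly by that rule, so the shortfall comes from the 5% of unrelated misses. This is why the reason for a gap matters.
- *Last completed diary taken as the end of effect when no return is recorded.* The mean is 5.4 to 5.7 weeks under permanent stopping, so the error runs the other way.

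**The case against.** **The diary is not named in the FIML sentence.** A reader might infer that the plan commits Aim 2 to FIML and so will lengthen duration. The documents do not support that as fact. The sentence concerns intention-to-treat analyses, whereas Aim 2 is a descriptive analysis of responders. FIML is only the one rule available to apply. If it does not apply, the diary has no missing-week rule, and the direction of the error depends on the rule chosen later, as the last-diary result shows. The overstatement is therefore conditional on FIML or censoring.

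**The behaviour is not evidenced.** Each participant has already done this test at screening with a score of 4 or higher, and is asked to repeat it at pretest and posttest. Return to pretest is thus a level she has met before. Background and Purpose does speak of "dyspareunia that renders sexual intercourse virtually impossible", but that is about intercourse. Anticipated risks tells women that "they don't need to answer any question they don't wish to answer", but that is about questionnaire items. Neither shows that tampon tests will be skipped. This stands, and it is why no size can be claimed for this trial.

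**Larger figures are easy to produce.** Suppose weekly return hazard h, with a fraction q of returns censored at the previous week. The Kaplan-Meier hazard is then h(1 − q) / (1 − qh). With a true median of 6 weeks, h = 1 − 2^(−1/6) = 0.109. For q = 0.25 and 0.5 the median becomes 8 and 12 weeks, and the week-12 share still benefiting becomes 35% and 49% instead of 25%. A reader might take these as the plan's bias. They are not, because the plan states no such censoring rule and the calculation assumes a woman who skips once never returns. FIML gave smaller shifts.

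**FIML does not fill in missing weeks.** It uses each woman's observed trend and the other women's courses, which limits the bias from isolated gaps. This stands and is reflected in the table.

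**The diary form is not in the documents.** It may already have a not-done field. If so, the analysis rule is still missing.

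**Conclusion.** The point holds as a conditional weakness of an exploratory aim. The Aim 2 score requires a pain-provoking act, return of that pain is the event, no reason for a missed insertion is described, and the one missing-data method is called unbiased without the condition it needs. If women with returned pain skip or stop before recording it, FIML or censoring overstates duration.

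The size in this trial is unknown. Under the assumed inputs it is small for isolated gaps (0.1 to 0.6 weeks) and material only if women stop altogether (0.6 to 2.7 weeks), against about 7.3 weeks.

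A reader might go further and infer that the arm comparison is biased. For Aim 2 that needs return or skipping to differ by arm, on which the documents say nothing. The Aim 1 comparison, made at posttest, does not use the weekly diary and is not challenged.

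**What to change.** 1. Add one diary field: *tampon not inserted or not completed: because of pain / other reason*. The reason cannot be recovered reliably afterwards, so it must be collected at the time.
2. Report Aim 2 duration, by arm and by vulvodynia type, in two ways: (a) FIML or censoring for all missed weeks; (b) weeks missed because of pain counted as pain returned to pretest, with FIML or censoring only for weeks missed for other reasons. Present (a) and (b) as a range, with neither as the sole main result.
3. In Data analysis, say whether the FIML rule covers the diary. For the diary data, drop the unconditional claim of unbiasedness and state the assumption about missing weeks.

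The cost is one extra field and a few sentences of analysis text. The downside is that (b) may understate duration if women skip for pain that is rising but still below pretest; this was not simulated, and it is why (b) should serve as one bound. Priority: a cheap improvement, for the exploratory aim only.

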**Title: DOUBLE-BLIND PHASE 2 RCT: EFFECT OF ACUPUNCTURE ON PATIENT VULVODYNIA OUTCOMES**

**RESEARCH PROTOCOL**

Dated 8/15/2017

sham procedure to mask both the acupuncturist and subject to the type of needle used. The acupuncturist will be well-trained in the study protocol and will be observed for fidelity. We will obtain measures at 2 time points (baseline and immediately post 10th acupuncture treatment [5 weeks]). Duration of effects will be measured weekly beginning one week after posttest for up to 12 weeks.

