**Exclusion criteria:**

Potential participants will be excluded if any of the following is true:

- a) infectious conditions
- b) inflammatory conditions
- c) neoplastic disorders
- d) neurologic disorders
- e) trauma to the genitals
- f) iatrogenic
- g) hormonal deficiencies
- h) co-morbid pelvic pain conditions (to avoid confounding pain outcomes)
- i) pelvic inflammatory disease
- j) endometriosis
- k) menopause
- l) pregnancy
- m) women receiving concurrent therapies that may decrease stress and/or muscle tension (i.e., concomitant physical therapy, biofeedback, massage, or other acupuncture sessions) will also be excluded

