**Safety monitoring:**

The study is low risk. However, the research team will monitor the safety of subjects during study procedures. In the event of injury related to this research, treatment will be available through the UIC Medical Center. However, the patient or third party payer, if any, will be responsible for payment of this treatment. Patient subjects will remain under the care of their usual provider, who will be available to give them usual care if needed. Any unanticipated problems related to the study procedure will be immediately reported to the IRB.

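### No treatment record is described for the 12 weeks after posttest, so pain held below pretest by a newly started therapy would count in Aim 2 as continuing acupuncture or placebo effect

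*Combined protocol and SAP*

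**What the plan says.** Aim 2 is set out under the specific aims. The population is defined as "In subjects with a clinically meaningful reduction in pain intensity (at least 1.5 points) at posttest compared to pretest", and the plan is to "describe the duration of the acupuncture treatment and placebo effects weekly until pain returns to pretest or up to 12 weeks after posttest". It will also "explore the duration of the effect by intervention group, vulvodynia subgroups, and demographic subgroups". Study design gives the schedule: "Duration of effects will be measured weekly beginning one week after posttest for up to 12 weeks".

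The instrument is described at the end of Procedures: after the tampon stimulus, women "complete the weekly vulvar pain diary to record their vulvar pain, so that we can determine the duration of the treatment effects". No other diary item is named.

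Other treatment appears in three places:

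- Procedures says PAINReportIt will "collect demographics and medications information". It is given at pretest and posttest, not during weekly follow-up.
- Exclusion criteria, item m, excludes "women receiving concurrent therapies that may decrease stress and/or muscle tension", with physical therapy, biofeedback, massage and other acupuncture as the listed therapies. The list is introduced as applying to potential participants.
- Safety monitoring says "Patient subjects will remain under the care of their usual provider, who will be available to give them usual care if needed".

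Data analysis deals with missing data (intention to treat, full information maximum likelihood). It has no rule for pain scores recorded after another treatment starts, and no method for Aim 2.

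**The concern.** Duration ends only when pain is back at the pretest level. Take a hypothetical woman who fell from 8 to 3 and has climbed back to 6. She still counts as having an effect, yet has reason to seek other care. If she starts something that works and never reaches 8 again, she is recorded as a 12-week effect, and nothing in the described data would show why.

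The protocol itself treats these therapies as a threat to the pain outcome, since it excludes women using them at entry. It also holds back the free real acupuncture for controls until after week 17. Study-provided acupuncture is thus kept out of the duration window, while outside treatment is neither addressed nor recorded.

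Aim 2 is meant to inform future research on initial and maintenance acupuncture, and durations that run too long would misinform it. The placebo arm does not remove the problem: start rates may differ by arm, and posttest responders are a subset formed after randomization. Treatment not recorded week by week is also hard to recover afterwards.

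**Working it through.** The plan gives no figure to reproduce: no expected duration, no expected rate of other treatment and no analysis method for Aim 2. All rates below are assumptions, chosen to show direction and rough size.

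**Model A: therapy starts at random times.** Weekly steps over 12 weeks.

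- True median duration *m* gives a weekly chance of pain return *h* = 1 − 0.5^(1/*m*). For *m* = 4, *h* = 0.159 and true week-12 persistence is 0.5^(12/4) = 12.5%.
- *C* is the 12-week chance of starting an effective therapy if pain has not yet returned, so the weekly chance is *c* = 1 − (1 − *C*)^(1/12).
- A starter is assumed to stay below pretest to week 12.
- With *q* = (1 − *c*)(1 − *h*), the share with no return and no new therapy is *q*^12 = (1 − *C*) × 12.5%. The share held down by new therapy is *c*(1 − *q*^12)/(1 − *q*). The diary shows their sum.

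| *C* | No return, no new therapy | Held by new therapy | Apparent week-12 persistence | Mean weeks within 12 (true 5.50) |
|---|---|---|---|---|
| 10% | 11.25% | 4.66% | 15.9% | 5.68 |
| 20% | 10.00% | 9.50% | 19.5% | 5.88 |
| 30% | 8.75% | 14.54% | 23.3% | 6.09 |
| 40% | 7.50% | 19.86% | 27.4% | 6.32 |

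With *m* = 8 the true 35.4% becomes 38.4% to 48.3% over the same range of *C*.

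**Model B: worst case.** A share *c* of responders starts exactly when pain would have returned, and the therapy works at once and never fails. Then S(t) = *c* + (1 − *c*) × 0.5^(t/4). For *c* = 10%, 20% and 40%:

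- week-12 persistence is 0.10 + 0.90 × 0.125 = 21%, 0.20 + 0.80 × 0.125 = 30%, and 0.40 + 0.60 × 0.125 = 47.5%;
- the observed median is 4.7, 5.7 and 10.3 weeks against a true 4.

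**Does censoring at the new treatment repair it?** Not under Model B, where returning pain prompts the start. The hazard estimated after censoring is (1 − *c*) times the true one, so the median is 4/(1 − *c*) = 4.4, 5.0 and 6.7 weeks. Week-12 persistence is 0.125^(1 − *c*) = 15%, 19% and 29% against 12.5%. Censoring is harmless only if starts are unrelated to the course of pain, which is the less likely case.

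**Does counting the start as end of effect repair it?** Under Model B it returns the true curve, because start and relapse coincide. Under Model A it gives the second column, 11.25% down to 7.5%, which is too short. If starts are fully reported and new treatments do not worsen pain, the observed and end-of-effect summaries therefore bracket the true duration.

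**The case against.** The case against is substantial, and much of it limits the point.

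- *The diary may record more than pain.* The form is not reproduced, and Procedures states its purpose, not a closed list of items. This stands: the concern is about the diary as described. Even if treatment is recorded, Aim 2 has no rule for using it.
- *Nothing says the excluded therapies may start.* Correct. Their availability in follow-up is inferred from silence, and the words concurrent and concomitant leave the time scope of item m open. The usual-care sentence stands beside text on research-related injury and is not a co-treatment policy. But it does leave usual care available, and no passage extends item m past entry.
- *Women have some reason to wait.* They stay blinded through the duration phase, and controls are promised free sessions afterwards. This may lower start rates but does not record them.
- *Effective alternatives are rare.* The protocol's own background says no therapy is proven and quick relief is uncommon. Both models assume that every new therapy works, so both lean high.
- *Aim 2 is exploratory.* True: it describes responders and tests no hypothesis. That limits the importance of the bias but does not remove it.

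A reader might go further and infer that Aim 1 is compromised, that 21% to 47.5% is the expected distortion, or that a difference between arms will be reversed. The documents support none of these. Treatment started after posttest cannot alter posttest scores. The higher range needs every assumption of Model B. The plan tests no contrast between arms in duration. Nor would prolonged relief in the placebo arm be credited to acupuncture, since Aim 2 describes placebo effects separately.

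**Conclusion.** The concern holds in a limited form. As described, follow-up collects pain and no treatment, and the duration rule would count pain held down by an effective new therapy as continuing acupuncture or placebo effect. If new treatments help at all, the error lengthens duration, and the planned data offer no way to estimate it.

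Its size is unknown. Under the random-start assumptions with a true median of 4 weeks, apparent week-12 persistence is about 16% to 27% instead of 12.5%, and mean duration within 12 weeks rises by 0.2 to 0.8 weeks (5.50 to between 5.68 and 6.32). If few women start other treatment, or what they start does not work, the effect is smaller. The primary and secondary posttest comparisons are untouched. This is a worthwhile, inexpensive improvement to an exploratory aim, not a flaw in the trial's main result.

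**What to change.** - Add one item to the weekly diary: whether any treatment for vulvar pain was started or changed that week, with its type and start date. If the form already has such an item, say so in Procedures.
- Tabulate new or changed treatment by arm and week among Aim 2 responders.
- In Data analysis, specify two summaries of duration: as observed, and with the first new treatment counted as end of effect. State that the second is a conservative reading.
- Do not rely on censoring at the new treatment. If a censored summary is shown, label the censoring as probably informative.

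No change to the Aim 1 analysis is needed on this ground, and no change to the care women may receive is proposed. The cost is a slightly longer diary, one extra table, and two duration summaries to explain instead of one.
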